2.1. Study Objectives

2.1.1. Primary Objective

The primary objective of the study is to assess the safety and tolerability of GRF6021, a human fraction administered by intravenous (IV) infusion, in subjects with Parkinson's disease (PD) and cognitive impairment.

2.1.2. Secondary Objectives

As a secondary objective, the study aims to assess the effects of GRF6021 on cognitive and motor function.

2.1.3. Exploratory Objectives

The exploratory objectives include blood and plasma collection to identify specific biomarkers associated with cognitive and motor function and/or indicators of PD with mild cognitive impairment (PD-MCI) and PD with dementia (PDD) progression. In addition, magnetic resonance imaging (MRI) of the brain will be conducted after the second dosing period in consenting subjects to identify potential therapeutic effects of GRF6021.

2.2. Study Endpoints

2.2.1. Safety Endpoints

2.2.1.1. Primary Safety Endpoints

The primary safety endpoints of this study include the following:

- Incidence of treatment-emergent adverse events (TEAEs) and serious adverse events (SAEs) identified by the Medical Dictionary for Regulatory Activities (MedDRA) preferred term (PT) and grouped by MedDRA System Organ Class (SOC).

2.2.1.2. Secondary Safety Endpoints

The secondary safety endpoints include the following:

- Change from baseline in clinical laboratory parameters.
- Change from baseline in vital sign measurements.
- Change from baseline in body weight.
- Change from baseline in the S-STs.

2.2.2. Efficacy Endpoints

2.2.2.1. Primary Efficacy Endpoint

Not Applicable.

2.2.2.2. Secondary Efficacy Endpoint(s)

The secondary efficacy endpoints of this study include the following:

- Change from baseline in the Montreal Cognitive Assessment (MoCA).
- Change from baseline in Continuity and Power of Attention, Working Memory, and Episodic Memory on the Cognitive Drug Research Computerized Cognition Battery (CDR-CCB).
- Change from baseline in Delis-Kaplan Executive Function System (D-KEFS) Verbal Fluency.
- Change from baseline in the Movement Disorder Society's Unified Parkinson's Disease Rating Scale (MDS-UPDRS) 1, 2, 3, and total score.
- Change from baseline in the Schwab and England Activities of Daily Living (SE-ADL) Scale.
- Change from baseline in the Clinical Impression of Severity Index – PD (CISI-PD).
- Change from baseline in the PD Quality of Life Questionnaire-39 (PDQ-39).
- Change from baseline in the Geriatric Depression Scale-15 (GDS-15).
- Change from baseline in the digital clock drawing test (dCDT).

2.2.2.3. Exploratory Efficacy Endpoint(s)

The exploratory efficacy endpoints of this study include the following:

- Serial compositional analysis of individual subject's plasma to identify specific biomarkers associated with cognitive functional changes and/or indicators of disease progression.
- Epigenetic changes.
- Change from baseline in the following assessments (in consenting subjects):
 - Brain morphometry as measured by MRI.
 - Functional connectivity as measured by task-free functional MRI (tf-fMRI), where available.
 - Cerebral blood flow assessments as measured by arterial-spin labeling (ASL) MRI, where available.

3. Overall Study Design and Plan

3.1. Overall Design

[figure not shown]
This is a randomized, double-blind, placebo-controlled study to assess the safety and tolerability of GRF6021, a [REDACTED] human [REDACTED] fraction, administered by IV infusion to subjects with PD and cognitive impairment.

All subjects will undergo a screening visit, including an MRI scan, baseline visit, 2 dosing periods, follow-up visits, and an end-of-study/early-termination visit. Each dosing period (Treatment 1, starting at Week 1; and Treatment 2, starting at Week 13) consists of 5 consecutive days ("pulsed dosing") of IV infusions of [REDACTED] of either GRF6021 or placebo. During each 5-day dosing period, subjects will reside in inpatient units and can be discharged after the fifth day of dosing. The subject participation period is approximately 7 months from Screening through End of Study, unless prematurely discontinued.

Safety and tolerability assessments will occur at every visit. Cognitive and motor testing will be performed at Baseline and at periodic interim visits following dosing.

The overall schema of the study is presented in Figure 1:

Figure 1: Study Schema

3.2. Sample Size and Power

A total of approximately 90 subjects will be randomized in a 2:1 ratio to active treatment (approximately 60 subjects) or placebo (approximately 30 subjects), with the intent of obtaining ~68 evaluable subjects who have received at least 5 doses and completed the study through Visit

8. Subjects who discontinue before completing Visit 8 may be replaced. Subjects who withdraw or are withdrawn during screening will be replaced.

The study is not statistically powered to detect differences in measures of clinical efficacy or biomarker endpoints. To evaluate potential safety signals, the statistical approximation described by Hanley (aka the “Rule of Threes” in which the upper bound of the 95% confidence interval [CI] for the frequency of an unreported AE is at most $3/n$ %, where n represents the number of subjects who received active GRF6021 in the study) will be used. In a sample of 60 subjects, the upper bound of the 95% CI for the frequency of an unobserved AE is approximately 5%. In addition, the proposed sample size may be sufficient to identify trends in efficacy endpoints that will be used to determine the appropriate sample size for subsequent studies.

3.3. Study Population

This study includes male and female subjects, aged 40-85 years old, with a diagnosis of either PD-MCI or PDD.

3.4. Treatments Administered

GRF6021 is a [REDACTED] human [REDACTED] fraction made from pooled human plasma product [REDACTED] that serves as a viable source of soluble, infusible plasma proteins from healthy male and female donors. It is administered by IV infusion of [REDACTED] to subjects. The placebo control agent will be 0.9% sodium chloride injection, USP (saline). Each infusion will have a duration of approximately [REDACTED] with a maximum of [REDACTED]. The infusion of active and placebo agents will be identical to maintain blinding. Subjects will receive one infusion of [REDACTED] per day for 5 consecutive days at Weeks 1 and 13.

3.5. Method of Assigning Subjects to Treatment Groups

Subjects will be randomized to GRF6021 (Group 1: active dosing in both dosing periods) or placebo (Group 2: placebo dosing in both dosing periods) in a 2:1 ratio. Randomization will be stratified by sex to ensure a balanced distribution of male and female subjects in both treatment groups. Subjects will be randomized at the conclusion of Visit 2, after eligibility has been confirmed (including MRI and echocardiography results).

3.6. Blinding and Unblinding

The following measures will be taken to ensure adequate allocation concealment during infusions: blinding of subjects, trial partners, study coordinators, physicians, and cognitive/motor test administrators to treatment allocation; use of blinded Outcomes Assessors and unblinded Infusion Nurses; and measures to block view of the vial or bag, infusion pump, IV tubing, and catheter throughout the infusion.

The study agent/placebo to be administered will be dispensed by an unblinded pharmacist (or other qualified personnel responsible for drug accountability) to an unblinded Infusion Nurse. Administration of the study agent/placebo will be performed by the unblinded Infusion Nurse, and all study outcome measures will be assessed by a blinded Outcomes Assessor.

To ensure that Outcomes Assessors, raters, and other study personnel, as well as subjects and trial partners are unaware of the allocation, appropriate measures will be taken to mask the study agent/placebo containers and IV setup such that they will only be visible as necessary to the unblinded Infusion Nurse. In addition, the vial and drip chamber will be covered with an opaque black bag or equivalent; a curtain, drape, or equivalent will be used to shield the infusion

administration setup; used vials/containers of the study agent or placebo will be concealed during transport and returned to the pharmacy at the end of the Infusion Period.

To avoid potential unblinding based on subject [REDACTED] levels, [REDACTED] lab results (aside from those tested at screening) will remain blinded until the conclusion of the study. Unblinding of [REDACTED] lab results would only occur for emergent safety reasons.

Communication between the blinded Outcomes Assessor and the unblinded Infusion Nurse will be restricted to only that required to ensure the immediate safety of subjects. Except for the designated personnel whose sole responsibility necessitates access to unblinding information (e.g. the unblinded CRA whose sole responsibility is to ensure study agent or placebo accountability, the unblinded clinical supply manager, etc.) and the unblinded statistician performing the interim analyses, the study Sponsor and their representatives will be blinded with respect to subjects' treatment allocation through database lock unless breaking the blind is required for safety reasons. The study blind can be broken for safety reasons if the information is required for the management of SAEs or severe AEs.

3.7. Schedule of Events

A detailed schedule of events for the study is provided in Table 1.

Table 1: Schedule of Events

	Screening ^a	Baseline Visit	Treatment ^b					Follow-up					Treatment ^{b,c}					Follow-up					End of Study/Early Termination Visit
			1	2	3	4	5	6	7	8	9	10	11	12	13	14	15	16	17	18	19		
Visit	1	2	3	4	5	6	7	8	9	10	11	12	13	14	15	16	17	18	19				
Infusion Number			1	2	3	4	5				6	7	8	9	10								
Day	Day -35 to -8	Day -7 to -1	1	2	3	4	5	6 + 3 days	7 + 7 days	8 ± 7 days	85 ± 7 days	86	87	88	89	90 + 3 days	112 ± 7 days	140 ± 7 days	168 ± 7 days				
Week			1					4								16		20	24				
Informed Consent/Optional MRI Consent	X																						
Medical History	X																						
Demographics	X																						
Vital Signs	X	X	X	X	X	X	X	X	X	X	X	X	X	X	X	X	X	X	X	X			
Physical Exam	X																						
Height	X																						
Weight	X		X ¹	X ¹	X ¹	X ¹	X ¹	X				X ¹	X ¹	X ¹	X ¹	X				X			
Suqne and Standing Blood Pressure ^d	X		X ¹	X ¹	X ¹	X ¹	X ¹	X				X ¹	X ¹	X ¹	X ¹	X							
12-lead ECG	X		X ¹	X ¹	X ¹	X ¹	X ¹	X				X ¹	X ¹	X ¹	X ¹	X							
Echocardiogram	X*																						
MRI	X*															X ¹							
Randomization																							
Targeted Physical Exam			X ¹	X ¹	X ¹	X ¹	X ¹				X ¹	X ¹	X ¹	X ¹	X ¹	X							
Concomitant Medication Review	X	X	X ¹	X ¹	X ¹	X ¹	X ¹	X	X	X	X ¹	X ¹	X ¹	X ¹	X ¹	X	X	X	X	X			
Adverse Event Review	X	X	X ¹	X ¹	X ¹	X ¹	X ¹	X	X	X	X ¹	X ¹	X ¹	X ¹	X ¹	X	X	X	X	X			
GRE6021/Placebo Infusion			X	X	X	X	X				X	X	X	X	X								
Blood/Urine Sampling																							
Screening Safety Lab Panel	X																						
Eat Safety Lab Panel																							
Pre-Infusion Safety Labs (performed onsite) ^f			X ¹	X ¹	X ¹	X ¹	X ¹				X ¹	X ¹	X ¹	X ¹						X			
Pregnancy Testing	X		X ¹	X ¹	X ¹	X ¹	X ¹				X ¹	X ¹	X ¹	X ¹									
Comprehensive Labs ^g											X ¹	X ¹	X ¹	X ¹									
Proteomics/Epigenetics/Bio banking			X ¹	X ¹	X ¹	X ¹	X ¹	X	X	X	X ¹	X ¹	X ¹	X ¹									
ApoE Genotype Testing			X ¹	X ¹	X ¹	X ¹	X ¹																
Cognitive and Motor Testing																							
MHIS	X																						
S-ST5	X																						
MoCA	X																						
Hoehn and Yahr																							
CDR-CCB	X																						
D-REFS	X ^a																						
hCDI	X																						
MDS-UPDRS 1/2/3	X																						
SE-ADL	X																						
CISL-PD	X																						
PDO-39	X																						
GDS-15	X																						

Notes:

*It is recommended, but not required, that the echocardiogram and screening MRI be performed after all other screening criteria have been met. The echocardiogram and screening MRI may be performed in any order.

X¹: To be performed prior to infusion start.

X ² : To be performed after infusion.
X ³ : To be performed post-infusion (approximately [REDACTED] after infusion start).
X ⁴ : If shipping of study agent to the study site will be required, subjects should be randomized at least 3 days prior to treatment start to ensure study agent availability.
a: The Screening Visit may be split to allow for sufficient time to complete all procedures. AEs and concomitant medications should be reviewed during split visits, as applicable.
b: The treatment window is 5 days. Visits 8 and/or 16 may occur 1-3 days later.
c: The visit window for Visit 11 is Day 85 ±7 days. Visits 12-15 should follow consecutively.
d: Blood pressure (BP) should be taken after the subject has been lying down for at least 10 minutes (supine). The subject should then stand for 3 minutes, and the BP should be taken again.
e: Includes all comprehensive labs, infectious serology (HIV, HBV, HCV), cobalamin (vitamin B12), pyridoxine (vitamin B6), thiamine (vitamin B1), TSH, direct antiglobulin test, BNP, serum IgA, haptoglobin, and C1 inhibitor (availability of C1 inhibitor lab results not required for evaluation of I/E criteria). Urine drug screen: cannabinoids, benzodiazepine, barbiturates, opiates, cocaine, amphetamines, methadone, phencyclidine, propoxyphene. Urinalysis: UPCR.
f: Includes all comprehensive labs, infectious serology, and direct antiglobulin test.
g: Samples for local pre-infusion labs should be collected and results interpreted PRIOR to the following day's infusion start. The following should be measured: sodium, potassium, ionized calcium, BUN, creatinine, hematocrit, hemoglobin, platelets.
h: Serum pregnancy test required at screening. Serum and/or urine pregnancy test may be used at subsequent timepoints. Results from pregnancy tests conducted at Visits 3 and 11 must be available prior to dosing.
i: Comprehensive labs: ALP, ALT, amylase, AST, bicarbonate, bilirubin (direct, indirect, and total), ionized calcium, chloride, cholesterol, LDL, HDL, CK, creatinine, GGT, glucose (random), iron, lactate dehydrogenase (LDH or LD), lipase, magnesium, phosphate, potassium, protein total, sodium, triglycerides, BUN, albumin, aPTT, PT/INR, CBC with differential (basophils, eosinophils, lymphocytes, monocytes, neutrophils). Urinalysis: blood, glucose, ketone, protein, pH, specific gravity, nitrite, leukocytes, bilirubin, urobilinogen, urine creatinine, urine albumin, albumin/creatinine ratio, urine sodium, sodium/creatinine ratio, urine potassium, potassium/creatinine ratio, and reflex urine microscopy if indicated.
j: The second, additional MRI will be performed in consenting subjects only and should be performed at Visit 16 + 7 days.

Task-free functional MRI and arterial-spin labeling MRI will be performed only at a subset of sites.
	
k: The CDR-CCB will require two training sessions prior to the baseline assessment. These training sessions can be performed at any time during the screening period.

---	--

4. Statistical Analysis and Reporting

4.1. Introduction

Data processing, tabulation of descriptive statistics, calculation of inferential statistics, and graphical representations will be performed primarily using SAS (release 9.4 or higher). If the use of other software is warranted, the final statistical methodology report will detail what software was used for what purposes.

Continuous (quantitative) variable summaries will include the number of subjects (n) with non-missing values, mean, standard deviation (SD), median, minimum, and maximum.

Categorical (qualitative) variable summaries will include the frequency and percentage of subjects who are in the particular category or each possible value. In general, the denominator for the percentage calculation will be based upon the total number of subjects in the study population for each treatment group, unless otherwise specified. The denominator for by-visit displays will be the number of subjects in the relevant study population with non-missing data at each visit.

The minimum and maximum will be reported with the same degree of precision (i.e., the same number of decimal places) as the observed data. Measures of location (mean and median) will be reported to 1 degree of precision more than the observed data and measures of spread (SD) will be reported to 2 degrees of precision more than the observed data.

Percentages will be presented to 1 decimal place, unless otherwise specified. Percentages will not be displayed when the numerator for a cell is 0.

Unless otherwise indicated, all statistical tests will be conducted at the 0.05 significance level using 2-tailed tests, and *P* values will be reported. Corresponding 95% CIs will be presented for statistical tests.

4.2. Interim Analysis and Data Monitoring

An unblinded interim analysis of the safety endpoints, including the primary endpoint and secondary safety endpoints, is planned when approximately 20 subjects have completed Visit 8 (end of first dosing period). The requirement that subjects remain in an inpatient unit during each dosing period was included in the protocol to enable safety monitoring during dosing. Once the Sponsor has reviewed the safety data from this interim analysis, the need for inpatient stays during dosing will be reassessed.

An unblinded interim analysis of the MoCA, CDR-CCB, and MDS-UPDRS Part 3 secondary efficacy endpoints is planned when approximately 40 subjects have completed Visit 8 (end of first dosing period). As the study is not powered for efficacy and no decisions will be made regarding stopping the trial, statistical testing will be performed at the 0.05 level using two-tailed tests on both the Evaluable and Per Protocol sets. To minimize potential bias of the remaining efficacy and safety data, only aggregated summary tables will be provided. The data will be provided in aggregate fashion so the difference between study agent and placebo is compared but individual treatment allocation remains blinded. An independent statistician other than the author of this plan will perform the unblinded analysis.

Safety will be monitored on an ongoing basis. If safety events of potential concern occur during the trial (i.e., 3 related events in the same SOC or a suspicious overall pattern), a Safety Evaluation Meeting will be triggered and an ad hoc interim safety analysis will be performed. Dosing may be temporarily halted based on the observations. The purpose of the meeting is for investigators, the Sponsor, external consultants with expertise relevant to the specific safety signal(s) detected as necessary, and the contract research organization (CRO) Medical Monitor(s) to discuss and evaluate the safety of the subjects using available aggregated safety data and without compromising study blinding, unless the Sponsor deems unblinding necessary for safety evaluation.

The results that will be presented for each interim analysis are flagged in the table of contents.

A separate analysis plan will be prepared for the CDR-CCB endpoints.

5. Analysis Sets

The following analysis sets are planned for this study:

- **Safety Set:** The Safety Set includes all subjects all subjects who receive at least 1 dose of the study agent. All safety analyses will be performed using the Safety Set, based on treatment received.
- **Intent-To-Treat Set (ITT):** The ITT Set includes all randomized participants. The presentation of baseline characteristics will be conducted on the ITT Set.
- **Evaluable Set:** The Evaluable Set includes all subjects who receive at least 5 of the 10 planned doses and complete through Visit 8. All efficacy analyses will be performed using the Evaluable Set, based on randomized treatment.
- **Per Protocol Set (PP):** The PP Set is a subset of the Evaluable set comprised of subjects who receive all 10 planned doses, who complete Visit 18 and Visit 19 in window, and who do not have any of the deviations listed below or any other deviation that could potentially affect the assessment of efficacy identified prior to database lock. Visit windows are found in Section 6.1.5. Deviations related to novel coronavirus disease 2019 (COVID-19) will also be evaluated in determining Per Protocol population eligibility prior to database lock. All efficacy analyses will be repeated in the Per Protocol Set, based on randomized treatment.
- **Complete Set:** The Complete Set is a subset of the PP Set comprised of subjects who did not have any changes to any of the following concomitant medications preferred terms reported at any time on study: Dopaminergic agents (e.g. Rotigotine [Neupro Patch], Duopa Pump, Sinemet [Carbidopa, Levodopa], Carbidopa, Rytary), Pregabalin (Lyrica), Amantadine, Antipsychotics (e.g. Pimavanserin Tartate [Nuplazid], Clozapine, Quetiapine Fumarate [Seroquel]), or benzodiazepines (e.g. Alprazolam). This includes those that were stable per protocol prior to first dose and either changed dose or stopped on study as well as those that began on study.

Deviation Type	Deviation	Major/Minor	Excluded from Per Protocol Set	Additional Clarification

Eligibility	I2. Diagnosis of clinically established or clinically probable PD according to MDS-PD criteria (Postuma 2015)(Appendix 8) with at least 1 year of PD symptoms	Major	Yes	
Eligibility	I3. Diagnosis of PD-MCI (Level I, i.e. impairment on a scale of global cognitive abilities validated for use in PD) or probable or possible PDD according to MDS criteria (Litvan 2012, Emre 2007)(Appendix 9)	Major	Yes	
Eligibility	I4. Score on the MoCA of 13-25, inclusive (Nasreddine 2005)(Appendix 1)	Major	Yes	
Eligibility	I5. Hoehn and Yahr Stages 1-4	Major	Yes	
Eligibility	I6. If on dopaminergic therapy (e.g., levodopa, dopamine agonists, monoamine oxidase inhibitors, catechol-O-methyl transferase inhibitors, amantadine), must be on stable dosage at least 4 weeks prior to baseline	Major	Yes	only if change in the last 2 weeks
Eligibility	I7. If on medications for cognition (e.g., rivastigmine, galantamine, donepezil, memantine), must be on stable dosage for at least 8 weeks prior to baseline	Major	Yes	only if change in the last 4 weeks
Eligibility	I8. If on antidepressant medications, must be on stable dosage for at least 8 weeks prior to baseline	Major	Yes	only if change in the last 4 weeks

Eligibility	I9. If on clozapine, quetiapine, or pimavanserin, must be on stable dosage for 8 weeks prior to baseline	Major	Yes	only if change in the last 4 weeks
Eligibility	I12. Modified Hachinski Ischemic Scale (MHIS) score of 4 or less (Rosen 1980)	Major	Yes	
Eligibility	E4. Treatment with any human blood product, including transfusions and IV immunoglobulin, during the 6 months prior to screening	Major	Yes	
Eligibility	E19. Positive urine drug screen. The presence of opioids, benzodiazepines, and/or amphetamines in the urine drug screen may be allowed if these are prescribed and the dose stable for at least 8 weeks prior to screening	Major	Yes	
Eligibility	E23. Concurrent participation in any other therapeutic treatment trial. If there was prior clinical trial participation, subject must have discontinued investigational agents for at least 30 days for small molecules, and 1 year for active or passive immunotherapies prior to screening	Major	Yes	
Eligibility	E24. If on deep brain stimulation (DBS), DBS surgery within 12 months of screening and/or a change in DBS settings within 12 weeks of screening. DBS settings must not be changed at any point during the subject's participation in the trial	Major	Yes	

Eligibility	E26. More than 2 lacunar strokes or other clinically relevant imaging abnormality on screening MRI	Major	Yes	
Eligibility	E27. Any other condition and/or situation that the investigator believes may interfere with the safety of the subject, study conduct, or interpretation of study data	Major	Yes	Only when interfering with the interpretation of study data
Compliance	Incorrect treatment dispensed and administered to subject	Major	Yes	
Out of Window	Efficacy Procedures performed outside of the protocol window which are a consistent pattern or potential risk to study data outcomes	Major	Yes	
Study Drug Temp Excursion	Study drug temperature excursions when determined to have impacted the quality of the study drug	Major	Yes	
Concomitant meds	Use of prohibited concomitant medications as defined in the protocol that have an effect on cognition	Case by Case		

6. General Issues for Statistical Analysis

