Aside from designated personnel whose sole responsibility necessitates access to unblinding information (e.g., the unblinded CRA whose sole responsibility is to ensure study agent/placebo accountability, the unblinded clinical supply manager, etc.), the Sponsor and their representatives will be blinded with respect to subjects' treatment allocation through database lock unless breaking the blind is required for safety reasons (see [10.6.3 Breaking the Study Blind/Subject Code](#)). The unblinded interim analyses will be performed by unblinded statisticians who are not members of the protocol study team. The data will be provided in aggregate fashion so the difference between study agent and placebo is compared but individual treatment allocation remains blinded.

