13.2. Efficacy Data Tabulations

Table 3: Efficacy Data

Number	Set	Title	Include in Interim Efficacy Analysis?
Table 14.2.1.1	Evaluable	Summary of Change from Baseline in MoCA Scores by Treatment	X
Table 14.2.1.2	Evaluable	Mean Change from Baseline in MoCA Total Score by Study Visit and Treatment, Tabulation of Fitted Summary Statistics from ANCOVA	
Table 14.2.1.3	Per Protocol	Summary of Change from Baseline in MoCA Scores by Treatment	X
Table 14.2.1.4	Per Protocol	Mean Change from Baseline in MoCA Total Score by Study Visit and Treatment, Tabulation of Fitted Summary Statistics from ANCOVA	
Table 14.2.1.5	Complete	Summary of Change from Baseline in MoCA Scores by Treatment	
Table 14.2.1.6	Complete	Mean Change from Baseline in MoCA Total Score by Study Visit and Treatment, Tabulation of Fitted Summary Statistics from ANCOVA	
Table 14.2.2.1	Evaluable	Summary of Change from Baseline in D-KEFS Total Score by Treatment	
Table 14.2.2.2	Evaluable	Mean Change from Baseline in D-KEFS Total Score by Study Visit and Treatment, Tabulation of Fitted Summary Statistics from ANCOVA	
Table 14.2.2.3	Per Protocol	Summary of Change from Baseline in D-KEFS Total Score by Treatment	

Number	Set	Title	Include in Interim Efficacy Analysis?
Table 14.2.2.4	Per Protocol	Mean Change from Baseline in D-KEFS Total Score by Study Visit and Treatment, Tabulation of Fitted Summary Statistics from ANCOVA	
Table 14.2.2.5	Complete	Summary of Change from Baseline in D-KEFS Total Score by Treatment	
Table 14.2.2.6	Complete	Mean Change from Baseline in D-KEFS Total Score by Study Visit and Treatment, Tabulation of Fitted Summary Statistics from ANCOVA	
Table 14.2.3.1	Evaluable	Summary of Change from Baseline in MDS-UPDRS Parts 1, 2, and 3 and Parts 1-3 Total Scores by Treatment	X
Table 14.2.3.2	Evaluable	Mean Change from Baseline in MDS-UPDRS Parts 1, 2, and 3 and Parts 1-3 Total Score by Study Visit and Treatment, Tabulation of Fitted Summary Statistics from ANCOVA	
Table 14.2.3.3	Per Protocol	Summary of Change from Baseline in MDS-UPDRS Parts 1, 2, and 3 and Parts 1-3 Total Scores by Treatment	X
Table 14.2.3.4	Per Protocol	Mean Change from Baseline in MDS-UPDRS Parts 1, 2, and 3 and Parts 1-3 Total Score by Study Visit and Treatment, Tabulation of Fitted Summary Statistics from ANCOVA	
Table 14.2.3.5	Complete	Summary of Change from Baseline in MDS-UPDRS Parts 1, 2, and 3 and Parts 1-3 Total Scores by Treatment	

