Min, Max		XX, XX	XX, XX	XX, XX

Continue for Dosing Period 1 and Dosing Period 2

Note Percentages are n/Number of subjects in the Safety Set*100. Subjects are summarized by treatment received.
[1] The duration of therapy for a subject to be considered evaluable is 5 exposure days.
SOURCE: Listing 16.2.5

Statistical Analysis Plan,
Sponsor Alkermest, Inc.
Protocol Number ALK6021-201
PCN Number ALKA7951

Table 14.2.1.1
Summary of Change from Baseline in MoCA Scores by Treatment
Evaluable Set

Parameter: Total Score	Placebo (N=XX)		GRF6021 (N=XX)	
	Observed	%CFB	Observed	%CFB
Baseline [1]				
n	XX		XX	
Mean (SD)	XX.X (XX.XX)		XX.X (XX.XX)	
Median	XX.X		XX.X	
Min, Max	XX, XX		XX, XX	
Week 4 (Visit 9)				
n	XX		XX	
Mean (SD)	XX.X (XX.XX)		XX.X (XX.XX)	
Median	XX.X		XX.X	
Min, Max	XX, XX		XX, XX	
P value [2]			X.XXXX	
Week 16 (Visit 17)				
n	XX		XX	
Mean (SD)	XX.X (XX.XX)		XX.X (XX.XX)	
Median	XX.X		XX.X	
Min, Max	XX, XX		XX, XX	
P value [2]			X.XXXX	

Repeat for all parameters.

Abbreviations: CFB = change from baseline; MoCA = Montreal Cognitive Assessment.
Note: Higher scores indicate better cognitive function; the total possible score is 30 and a score of 26 or more is considered normal. A positive value of change means an improvement, and a negative value of change means deterioration. Subjects are summarized by randomized treatment.

[1] The baseline value is the MoCA Score from Visit 1 (Screening).

[2] P-value for testing mean change from baseline to subsequent visit is 0 is calculated using a paired t-test.

SOURCE: Listing 16.2.5.1

Programming note: Check normality per Section 8.2 of the SAP. If the data are non-normal, use the Wilcoxon signed-rank test and update the footnote accordingly. Parameters will be: visuospatial/executive, naming, memory, attention, language, abstraction, delayed recall, orientation.

Table 14.2.1.2
Mean Change from Baseline in MoCA Total Score by Study Visit and Treatment
Tabulation of Fitted Summary Statistics from ANCOVA
Evaluable Set

Study Visit Statistic [1]	Placebo (N=XX)	GRF6021 (N=XX)
Week 4 (Visit 9) n	XX	XX
LS Mean Change from Baseline (SE) (95% CI for LS Mean Change from Baseline) P value for LS Mean Change from Baseline) [2]	XX.X (X.XX) (XX.X, XX.X) X.XXXX	XX.X (X.XX) (XX.X, XX.X) X.XXXX
LS Mean Difference from Placebo (SE) (95% CI for Difference from Placebo) P value for Difference from Placebo [3]		XX.X (X.XX) (XX.X, XX.X) X.XXXX
Week 16 (Visit 17) n	XX	XX

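### For MoCA and MDS-UPDRS, the efficacy interim is said to compare GRF6021 with placebo, but the tables flagged for it test only each arm's own change from baseline

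*SAP*

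**What the plan says.** SAP 4.2 states that "An unblinded interim analysis of the MoCA, CDR-CCB, and MDS-UPDRS Part 3 secondary efficacy endpoints is planned" once about 40 subjects have completed Visit 8, and that "statistical testing will be performed at the 0.05 level using two-tailed tests on both the Evaluable and Per Protocol sets". The data are to be given in aggregate "so the difference between study agent and placebo is compared". Protocol 10.6.1 gives the same purpose for the unblinded interims: "so the difference between study agent and placebo is compared but individual treatment allocation remains blinded".

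SAP 4.2 then fixes the content of the interim: "The results that will be presented for each interim analysis are flagged in the table of contents". Those flags are in the interim column of SAP 13.2, Table 3. The MoCA and MDS-UPDRS summary tables on the Evaluable and Per Protocol Sets are marked. The ANCOVA tables, such as "Mean Change from Baseline in MoCA Total Score by Study Visit and Treatment, Tabulation of Fitted Summary Statistics from ANCOVA", are not.

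The shell for the marked tables is that of Table 14.2.1.1 (SAP 14.2). It shows placebo and GRF6021 in adjacent columns. Its one inferential footnote reads: "P-value for testing mean change from baseline to subsequent visit is 0 is calculated using a paired t-test". A signed-rank test replaces the t-test if the data are not normal.

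**The concern.** A test of each arm's own change against zero does not use the randomised control. Change common to both arms counts in full towards the GRF6021 P value. Repeat testing could produce such change. So could regression to the mean: eligibility restricts MoCA to 13 to 25, and the same screening score serves as the MoCA baseline.

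The 2:1 allocation adds an asymmetry. For an identical true change, the larger GRF6021 arm reaches P<0.05 more often than placebo. A result that is significant on active and not on placebo then looks like a treatment signal when there is none.

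The stated property, a comparison of study agent with placebo supported by testing at 0.05, is therefore not delivered for these two scales by the outputs the SAP prescribes. SAP 4.1 also says 95% confidence intervals accompany statistical tests; the flagged shell has none.

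**Working it through.** **Step 1: match the flags to the tables (SAP 13.2, Table 3).**

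| Scale and set | Summary table | Flagged | ANCOVA table | Flagged |
|---|---|---|---|---|
| MoCA, Evaluable | 14.2.1.1 | yes | 14.2.1.2 | no |
| MoCA, Per Protocol | 14.2.1.3 | yes | 14.2.1.4 | no |
| MDS-UPDRS, Evaluable | 14.2.3.1 | yes | 14.2.3.2 | no |
| MDS-UPDRS, Per Protocol | 14.2.3.3 | yes | 14.2.3.4 | no |

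All four summary tables are flagged and none of the four ANCOVA tables is. The SAP document history for version 3.0 says the marks were taken off the ANCOVA tables because those tables had not been provided at the interim. The missing flags are therefore deliberate and not an artefact of a broken table.

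**Step 2: match the tables to their tests (SAP 14.2).** The three other flagged tables reuse the shell of 14.2.1.1, whose only P value is for change against zero. The P value and confidence interval for GRF6021 minus placebo are in the shell of 14.2.1.2, which only the ANCOVA tables use. The rank-sum comparison in SAP 8.2 has no row in the flagged shell. Tables 14.1.2.1 and 14.3.1.1 are also flagged for the efficacy interim and do contain between-arm P values, but for baseline characteristics and adverse events.

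**Step 3: illustrate the consequence.** The plan gives no operating figure for this interim, so there is none to reproduce. Inputs:

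- Size: about 40 subjects (SAP 4.2).
- Allocation: 2:1 (SAP 3.2), so 40 × 2/3 = 26.7 and 40 × 1/3 = 13.3, taken as 27 and 13.
- Level: two-sided 0.05 (SAP 4.2).
- Assumed, because the documents give no placebo change: the same true change d in both arms, in SD units of change, from 0 to 0.5, and no treatment effect.

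The within-arm chance of significance comes from the noncentral t distribution with n − 1 degrees of freedom and noncentrality d√n. The arms are independent, so P(active only) = P(active) × [1 − P(placebo)]. At d = 0.3 this is 0.324 × (1 − 0.169) = 0.269.

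| Shared change d | GRF6021 significant | Placebo significant | GRF6021 only | Exactly one arm |
|---|---|---|---|---|
| 0 | 5.0% | 5.0% | 4.8% | 9.5% |
| 0.2 SD | 17.0% | 10.2% | 15.3% | 23.8% |
| 0.3 SD | 32.4% | 16.9% | 26.9% | 38.3% |
| 0.4 SD | 51.7% | 26.4% | 38.0% | 50.8% |
| 0.5 SD | 70.6% | 38.2% | 43.6% | 54.9% |

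Subtracting the fourth column from the fifth gives placebo only: 8.5% at 0.2 SD and 11.3% at 0.5 SD, so the imbalance favours GRF6021. A simulation of 40,000 trials per scenario gave 15.3%, 27.0%, 37.7% and 43.6% for GRF6021 only, for d from 0.2 to 0.5.

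**Step 4: the between-arm test at the same size.** The shared change cancels, so its false-positive rate stays at 5% (4.8% to 5.2% in the simulation). The standard error of the difference is √(1/27 + 1/13) = 0.338 SD. By normal approximation the 95% CI half-width is 1.96 × 0.338 = 0.66 SD, and the difference detectable with 80% power is (1.96 + 0.84) × 0.338 = 0.95 SD. Within-arm P values do not convey that imprecision.

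**Step 5: limit on the numbers.** The trigger is completion of Visit 8, but the first post-dose MoCA is at Visit 9 (SAP 8.2.1). For MoCA, 27 and 13 are upper limits.

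**The case against.** The strongest reply is that the quoted sentence describes how data are released without revealing individual allocation; in the protocol it stands under masking procedures. The flagged tables put the arms side by side with n, mean and SD, so a descriptive comparison is possible. Protocol 10.4.3 attaches the two-tailed 0.05 level to paired within-subject tests and says only that between-group differences may be assessed. Protocol 10.2 calls the efficacy approach primarily descriptive.

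This has weight, but a side-by-side display supplies neither a between-arm test nor an interval. SAP 4.2 speaks of comparing study agent with placebo and of testing at 0.05 in the same paragraph, and nowhere says the testing is confined to within-arm change.

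Other points in reply stand:

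- The interim outputs already exist. Adding flags to Table 3 without running the tables would misstate what was delivered.
- The SAP says no stopping decision will follow, and the final analysis compares the arms by ANCOVA.
- The shared changes in the illustration are assumed. A reader who looks at the means as well as the P values is less easily misled.
- The within-arm tests are prespecified, so their presence is not itself an error.

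A reader might go further and infer that the interim's testing never compares the randomised arms. The documents do not support that. CDR-CCB is one of the three interim endpoints, and its plan appears here by title only, so a between-arm test there cannot be ruled out. Nor do they say that this interim was meant to show trends; that language belongs to the full sample size and the secondary efficacy analysis.

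**Conclusion.** The point holds for MoCA and MDS-UPDRS. The SAP and protocol describe an interim comparison of GRF6021 with placebo, and the SAP sets 0.05 testing, yet the prescribed tables for these scales contain only within-arm tests.

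The consequence is one of interpretation. No type I error for stopping is at stake, and the final between-arm analysis is untouched. Under an assumed shared change of 0.2 to 0.5 SD, no treatment effect and at most 27 and 13 subjects, the misleading pattern of active significant and placebo not arises in about 15% to 44% of trials, against 5% for a between-arm test. The percentages depend on that assumed range and would differ with fewer MoCA observations. The mismatch between the stated comparison and the flagged tables depends on neither. It should be corrected, but it is not critical to the trial's conclusions.

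**What to change.** Because the ANCOVA tables were not provided at the interim, choose one of two routes.

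(a) Produce the GRF6021-minus-placebo difference with 95% CI for MoCA total score and MDS-UPDRS Part 3 from the same interim data cut, labelled as added later. MoCA already has a model in SAP 8.2.1. SAP 8.2.4 fits the MDS-UPDRS total only, so its model (with baseline score and age as covariates) must be extended explicitly to Part 3.

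(b) Correct SAP 4.2 and Section 10 (Changes from Planned Analysis) to say that interim testing of these two scales was within-arm with a descriptive between-arm display, and state what was done for CDR-CCB.

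Under either route, add a sentence that the interim within-arm P values are not evidence of a GRF6021 effect.

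Route (a) costs a little programming by the unblinded statistician and yields a wide interval, about ±0.66 SD at best. Route (b) costs wording only.
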